1.2 How will you define serious adverse events?

_X_A serious adverse event will be considered any undesirable sign, symptom, or medical condition which is fatal, is life-threatening, requires or prolongs inpatient hospitalization, results in persistent or significant disability/incapacity, constitutes a congenital anomaly or birth defect, is medically significant and which the investigator regards as serious based on appropriate medical judgment. An important medical event is any AE that may not result in death, be life-threatening, or require hospitalization but may be considered an SAE when, based upon appropriate medical judgment, it may jeopardize the patient and may require medical or surgical intervention to prevent one of the outcomes listed in the definitions of SAEs.

1.3 What is the definition of an unanticipated problem?

Do not change this answer

An unanticipated problem is any event, experience that meets ALL 3 criteria below:

- Is unexpected in terms of nature, severity or frequency given the research procedures that are described in the protocol-related documents AND in the characteristics of the subject population being studies
- Related or possibly related to participation in research. This means that there is a reasonable possibility that the incident may have been caused by the procedures involved in the research study.
- The incident suggests that the research placed the subject or others at greater risk of harm than was previously known or recognized OR results in actual harm to the subject or others

1.4 What are the definitions of a protocol violation and/or noncompliance?

Do not change this answer

A **protocol violation** is defined as any change, deviation, or departure from the study design or procedures of research project that is NOT approved by the IRB-HSR prior to its initiation or implementation. Protocol violations may be major or minor violations.

Noncompliance can be a protocol violation OR deviation from standard operating procedures, Good Clinical Practices (GCPs), federal, state or local regulations. Noncompliance may be serious or continuing.

Additional Information: see the IRB-HSR website at

http://www.virginia.edu/vpr/irb/HSR_docs/Forms/Protocol_Violations_%20Enrollment_Exceptions Instructions.doc

1.5 If pregnancy occurs how will this information be managed?

__X__ Adverse Event- will follow adverse event recording and reporting procedures outlined in section 3.

1.6 W	nat is the	definition	of a Protocol	Enrollment	Exception?
-------	------------	------------	---------------	------------	-------------------

X NA- No outside sponsor

1.7 What is the definition of a data breach?

Do not change this answer

A data breach is defined in the HITECH Act (43 USC 17932) as an unauthorized acquisition, access, or use of protected health information (PHI) that compromises the security or privacy of such information.

Additional Information may be found on the IRB-HSR Website: Data Breach

2. Identified risks and plans to minimize risk

2.1 What risks are expected due to the intervention in this protocol?

Expected Risks related to study	Frequency
participation.	
Violation of subject's privacy and	Minimized due to the requirements
confidentiality	of the privacy plan in this protocol
Risk of infection from surgical	Occurs rarely
procedure	
Slight discomfort due to knee	Occurs rarely
examination procedures	
Risks from radiography (x-ray)	Occurs rarely
Risk that patients may be sore following	Occurs rarely
the strength or gait protocols	
Risk of discomfort from electrical	Occurs rarely
stimulation during superimposed burst	
testing	

2.2 List by bullet format a summary of safety tests/procedures/observations to be performed that will minimize risks to participants:

- Review of medical history
- Review of eligibility criteria
- Adverse event monitoring at each visit
- Review of self-reported function at each visit
- Post-surgical care/ education (before and after surgery)

2.3 Under what criteria would an INDIVIDUAL SUBJECT'S study treatment or study participation be stopped or modified

X At subject, PI or sponsor's request

Page 14 of 41

2.4 Under what criteria would THE ENTIRE STUDY need to be	e stopped
---	-----------

INS	TRL	JCT	IO	NS:
				,

3.

- These are called stopping rules for early termination of the entire study.
- List criteria regardless of whether the study is sponsored or not.
- Be sure to include any criteria for which the UVa PI would halt the study at UVa.
- Check all that apply.
- X Per IRB, PI, DSMB, or sponsor discretion

2.5 What are the criteria for break	ing the blind/mask?
XOther: If deemed to imp	act clinical care
2.6 How will subject withdraws	als/dropouts be reported to the IRB prior to study completion?
XIRB-HSR continuation statu	us form
Adverse Event / Unanticipated Pro	oblem Recording and Reporting
3.1 Will all adverse events, as defin	ned in section 1.1, be collected/recorded? No used?
xOnly adverse ev	ents that are deemed related AND serious

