Although extensive research has been carried out on ACL Femoral Tunnel placement, very little attention has been given to the tibial tunnel. Staubli et al. suggest that the tibial tunnel be placed in the center of the ACL footprint, which they described as being approximately 43% of the way (anterior to posterior) across the proximal tibia at its widest extent. However, others have suggested that a more anterior placement may yield improved biomechanical and clinical results. The center of the ACL footprint and the posterior aspect of the anterior horn of the lateral meniscus does not yield tibial tunnel placement a consistent percentage of the way across the tibial plateau⁴, therefore, guidelines should be based on intraoperative fluoroscopic measurements. However, the question remaining is what percentage of the A-P distance across the tibia is the ideal location for the tibial tunnel in ACL reconstruction. This study will help answer that question.

Page 4 of 41

Hypothesis to be Tested

Objective:

Compare anterior versus posterior tibial tunnel placement for ACL reconstruction in a prospective randomized clinical trial.

Hypotheses:

A more anterior placed tibial tunnel will yield improved outcomes with regard to:

- 1. Improved knee-specific self-reported function (IKDC)
- 2. Decreased knee joint laxity (KT-1000)

Study Design: Biomedical

- 1. Will controls be used? No
- 2. What is the study design?

Single-blind, randomized controlled clinical trial

3. Does the study involve a placebo? No

Human Participants

Ages: 16-50

Sex: Male and Female

Race: All

Subjects- see below

INSTRUCTIONS: For question 1-4 below insert an exact #. Ranges or OPEN is not allowed. This # should be the maximum # you expect to need to enroll (i.e. sign consent) If you are only collecting specimens the number of participants should equate to the # of specimens you need. If you are collecting only data from a chart review the number should designate the number of subjects whose medical records you plan to review. Age/ Sex/Race criteria should designate the demographics of participants from whom you will obtain the specimen/data.

- **1.** Provide target # of subjects (at all sites) needed to complete protocol.75(prospective aspect) 45 for retrospectice (UVA only)
- 2. Describe expected rate of screen failure/ dropouts/withdrawals from all sites.

We expect up to a 20% rate of attrition due to loss of follow up.

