Sample size for IKDC and KT-1000 side-side differences are calculated based on the expected between-group differences observed at the final time point of this study – 24 months post reconstruction. In order to observe a 2.4 mm between group differences in joint laxity symmetry, we need 40 patients per group. This estimate accounts for up to 3.5 mm in variability in KT-1000 side-side measurement change from pre-post-surgery. Further, we need 55 patients per group to detect a 8-point difference in IKDC score between groups assuming variability of 12 points in IKDC score. These estimates account for 20% attrition. Estimates are calculated to find statistically significant differences allowing for 5% type I error rate and power exceeding 80%.

4. What is your plan for primary variable analysis?

We will use independent t tests to determine group differences at each time point.

Page 7 of 41

5. What is your plan for secondary variable analysis?

We do not plan to use a secondary variable analysis.

6. Have you been working with a statistician in designing this protocol? Yes **IF YES, what is their name?** [name]

Page 8 of 41

- 7. Will data from multiple sites be combined during analysis? Yes
 - 7(a). Does the study involve randomization? Yes

IF YES, will randomization be done at each site or among sites? Randomization will be done at each site.

- 7(b). Has the sample size calculation considered the variation among sites? Yes
- 7(c). When combining the data from multiple sites to assess the study results, is the effect of the treatment to be tested (or the association to be tested) assumed to be the same across sites or vary among sites? What is the modelling strategy?

Yes. The effect of the treatment (placement of tibial tunnel) will be assessed using standard measures of joint laxity and patient-reported function. We have no evidence to believe that these outcomes differ between sites under standard protocols.

7(d). Is there a common protocol used in all sites? NO

IF NO, how will differences among sites, such as those related to the implementation, inclusion criteria, patient characteristics, or other sites characteristics, be considered to assess the study results?

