Potential subjects will be identified, screened, and eligibility criteria reviewed in a similar manner at each institution. Each practice will follow the same criteria for enrollment. Statistical considerations will be employed following the completion of data collection to account for differences in patient characteristics/ demographics.

Biomedical Research

1. What will be done in this protocol?

Study Procedures:

All procedures apply to subjects who enter the study prior to surgery.

Screening visit (Visit 1)

After written informed consent is obtained, initial screening will consist of a thorough medical history and physical examination. Special attention will be given to inclusion and exclusion criteria as listed above. Only patients who meet all inclusion and exclusion criteria will be allowed to continue to baseline outcomes data collection. The following subjective outcomes and clinical examination data will be collected at each session.

Subjective Outcomes (10 minutes)

- International Knee Documentation Committee (IKDC) Subjective Knee Evaluation
- Marx Activity Rating Scale

Page 9 of 41

X-ray (15 minutes)

Standing 2-view (posterior-anterior, lateral)

Clinical Evaluation (10 minutes)

- Knee joint laxity with KT-1000
- Knee joint range of motion
- Thigh circumference (15 cm above knee cap)

Surgery (Visit 2)

• Record surgical details: procedure(s) performed, time of procedure, tunnel diameter, tunnel placement details, other arthroscopic findings pertinent to case

Follow Up Visits (Visits 3-5)

Subjects who enter the study after surgery will complete the visits below based upon when they enter the study from their surgery date. If subjects are unable to come to UVA for the follow up visits, it is possible to arrange a home visit with a member of the study team to collect outcomes. Please note that we can only collect questionnaires and the KT-1000 ligament laxity measurement of the knee exam through a home visit.

- 6 months (approximately 182 ± 14 days following surgery)
 - Review of criteria for enrollment
 - Record adverse events
 - Clinical evaluation
 - KT-1000 Ligament Laxity Assessment Questionnaires
 - Marx Activity Scale
 - IKDC Subjective Questionnaire
- 12 months (approximately 364 ± 21 days following surgery)
 - Record adverse events
 - Standing 2-view (posterior-anterior, lateral) x-ray
 - Clinical evaluation
 - o KT-1000 Ligament Laxity Assessment
 - Questionnaires
 - Marx Activity Scale

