 - **X**_This imaging research examination utilizes the same imaging techniques, equipment, scanning sequences that would be used if the subject were to have the imaging performed for clinical care. There exists the potential for the discovery of clinically significant incidental findings.
 - ► If checked, answer the following:

Will the images be read by a licensed radiologist and the reading placed in the subject's medical record? Yes

- 6. Will you be using viable embryos? No
- 7. Will you be using embryonic stem cells? No
- 8. Are any aspects of the study kept secret from the participants? Yes
 - ► IF YES, describe:

Group assignment will remain confidential until the end of the study

- 9. Is any deception used in the study? No
- 10. If this protocol involves study treatment, explain how a subject will be transitioned from study treatment when they have completed their participation in the study.

All subjects will be prescribed the same rehabilitation program and guidelines in accordance with the standard of care post ACL reconstruction procedure. Participating in this study will not affect the care given or prescribed in any way.

Data and Safety Monitoring Plan

INSTRUCTIONS:

If you have any questions completing this section call [name] for assistance.

A Sponsor is defined as entity that will receive data prior to publication.

- 1. Definition:
 - 1.1 How will you define adverse events (AE)) for this study?
 - __X__An adverse event will be considered any undesirable sign, symptom or medical or psychological condition **even if the event is not considered to be related** to the investigational drug/device/intervention. Medical condition/diseases present before starting the investigational drug/intervention will be considered adverse events only if they worsen after starting study treatment/intervention. An adverse event is also any undesirable and unintended effect of

Page 12 of 41

research occurring in human subjects as a result of the collection of identifiable private information under the research. Adverse events also include any problems associated with the use of an investigational device that adversely affects the rights, safety or welfare of subject s.

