3.2 How will adverse event data beXPaper AE forms/source of	
XSpreadsheet: paper or el	lectronic
3.3. How will AEs be classified/gra	ded?
X Serious/Not serious Requ	ired for all protocols
3.4 What scale will the PI use wh participation?	en evaluating the relatedness of adverse events to the study
XThe PI will determine the using the following scale:	e relationship of adverse events to the study
Possibly related: A	AE is clearly related to the intervention AE may be related to the intervention AE is clearly not related to intervention

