	5.1. Who is responsible for overseeing safety data for this study?
	XNo additional oversight body other than PI at UVa Skip question 5.2
	5.2. What is the composition of the reviewing body and how is it affiliated with the sponsor? N/A
	5.3. What items will be included in the aggregate review conducted by the PI?
	XAll adverse events

IRB-HSR#17922: Tibial Tunnel Placement for ACL Reconstruction: A Prospective, Randomized Controlled **Clinical Trial** __X__Unanticipated Problems __X__Protocol violations/Issues of noncompliance X Audit results Application of dose finding escalation/de-escalation rules These should be outlined under 2.4. Application of study designed stopping/decision rules __X__Early withdrawals X Whether the study accrual pattern warrants continuation/action X Endpoint data 5.4 How often will aggregate review occur? For additional information on aggregate review see: www.virginia.edu/vpr/irb/hsr/continuations.html#aggreview Per Enrollment/Events X Annually Semi-Annually ____Quarterly Monthly 5.5. How often will a report, regarding the outcome of the review by the DSMB/DSMC, be sent to the UVa PI? N/A 5.6. How will a report of the information discussed in question 5.4 OR 5.5 be submitted to the IRB? X Part of IRB-HSR continuation status form **Collaborative Site Analysis Studies** 1. List the sites that will be sharing data/specimens. Jordan-Young Institute Orthopedic Surgery and Sports Medicine 2. Will any data/specimens be sent to UVa for analysis from the sites outside of UVa? Yes ▶ IF YES, do you confirm you will have received a copy of the IRB approval from the outside

3. Do you confirm you will have a Material Transfer Agreement (MTA) through the Grants and Contracts office prior to sending or receiving data/specimens? Yes

site before receiving data/specimens from them? Yes

4. Describe the process for sharing safety concerns.

Frequent communication will occur between sites in the form of monthly emails and quarterly conference calls. The PI, study coordinators, and any appropriate sub-investigators will be involved in this communication.

	Collaborative Site Analysis Studies DSMP				
Type of Event	To whom will it be reported:	Time Frame for Reporting	How reported?		
*Serious, unexpected and related or possibly related adverse events	All Research Sites	Within 15 days after the site PI receives knowledge of the event.	IND/IDE Safety Report (Cover letter, copy of MedWatch/narrative)		

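### Section 3.1 records only adverse events judged both related and serious; this conflicts with the visit schedule and section 5.3, and can leave graft re-ruptures and some reoperations unrecorded as events

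*Combined protocol and SAP*

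**What the plan says.** All references are to the combined protocol and SAP.

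- **Data and Safety Monitoring Plan, 3.1.** Asked whether all adverse events as defined in 1.1 will be recorded, the plan answers no and keeps only those "that are deemed related AND serious".
- **Same plan, 1.1.** The definition is broad and covers events whether or not they are thought related to the intervention.
- **Follow Up Visits.** The 6-, 12- and 24-month visits each carry the instruction "Record adverse events", with no limit by relatedness or seriousness.
- **Same plan, 5.3 and 5.4.** All adverse events are among the items the PI reviews in aggregate once a year. Section 5.1 names no oversight body beyond the PI.
- **Same plan, 3.3 and 3.4.** Events are classed as serious or not serious, and the PI grades relatedness on a three-level scale that includes a clearly-not-related level.
- **Study Design and Biomedical Research, item 8.** The design is "Single-blind, randomized controlled clinical trial". On what is withheld from participants, the plan says "Group assignment will remain confidential until the end of the study".

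**The concern.** The recording rule in 3.1 is narrower than the visit instruction and the annual review that depend on it. If staff follow 3.1, the PI cannot review all events as 1.1 defines them, because most classes of event were never collected. The not-serious and not-related classes in 3.3 and 3.4 would also stay empty.

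Two things are at stake.

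- **Events in the operated knee.** The trial compares tunnel positions through laxity and function of a reconstructed knee at 24 months. A re-rupture or reoperation in that knee bears directly on both measures, and 3.1 makes its capture depend on two judgments.
- **Who makes the relatedness judgment.** It is the PI's. The envelope is opened during surgery, so the treating surgeon knows the arm. The documents keep assignment from participants but do not say that the PI is masked. A filter applied with knowledge of the arm could work differently in the two arms.

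**Working it through.** There is no plan figure to reproduce, and the point does not depend on alpha, power, effect size or sample size. The check is a comparison of the text.

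**Step 1: what 3.1 keeps.** Both conditions must hold.

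| Judged by the study team | Serious | Not serious |
|---|---|---|
| Related | recorded | not recorded |
| Unrelated | not recorded | not recorded |

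A re-rupture attributed to new trauma falls in the bottom row and is not recorded even if serious. A reoperation judged not serious falls in the right-hand column and is not recorded even if related.

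**Step 2: what the other sections require.** The visit schedule, read as worded, keeps all four cells. Section 5.3, using the term as 1.1 defines it, needs all four cells for review. Neither can be met from the one cell that 3.1 keeps.

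**Step 3: whether another route fills the gap.**

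- *Serious-event definition (1.2).* It includes medically significant events and those that may need surgical intervention, subject to judgment. Some reoperations would count as serious, but they would still have to be judged related.
- *Unanticipated problems (1.3).* There is no seriousness threshold, but the event must be unexpected, related or possibly related, and harmful or indicative of greater risk. This reaches some related, non-serious events. It does not reach expected or clearly unrelated ones.
- *Surgical details.* These are specified for the index operation (Visit 2) only.
- *Review of enrollment criteria.* It is listed at 6 months and not at 12 or 24.
- *X-rays at 12 and 24 months; diagnoses, procedures and operative notes from the UVA data repository.* These may reveal an event, but none is specified to record re-rupture or reoperation by arm.
- *Home visits.* Only questionnaires and KT-1000 can be collected, and adverse event recording is not listed.
- *Analysis plan.* It specifies independent t tests at each time point and no secondary analysis. It says nothing about knees revised before 24 months.

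**Step 4: whom 3.1 covers.** Human Participants, item 4, gives up to 90 prospective participants, 55 of them at UVA, and 45 retrospective participants at UVA. So 55 + 45 = 100 consent under this protocol, and 90 − 55 = 35 prospective participants are at the other site. Statistical Considerations 7(d) reads "Is there a common protocol used in all sites? NO", and the other site's recording rule is not shown. The gap is therefore demonstrated for the UVA protocol only.

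**The case against.** The strongest reply is that there is no real conflict. The visit instruction can be read as shorthand applied under 3.1, and 1.5 sends pregnancy to the recording procedures of section 3, which suggests that section 3 is the operative rule. Section 5.3 could likewise be read as all events that happen to be recorded. These readings soften the wording conflict, but they confirm the gap: if 3.1 governs everywhere, the bottom row of the table is lost by design.

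Other parts of the reply stand and limit the point.

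- **Section 2.2.** A reader might cite "Adverse event monitoring at each visit" as a further contradiction. It speaks of monitoring, not recording, so it does not conflict with 3.1.
- **Possibly related events.** A reader might infer that 3.1 excludes them, because 3.4 has a separate level ("AE may be related to the intervention") and the collaborative-site table names "Serious, unexpected and related or possibly related adverse events". The documents do not support that. Section 3.1 does not say either way, the text around 3.1 and 3.4 is damaged, and the table governs reporting between sites. A duty to report such events suggests, if anything, that they are recorded.
- **Reoperations.** A reader might infer that all of them are lost. Sections 1.2 and 1.3 would catch some, so reoperation is the weaker of the two examples.
- **Breadth of remedy.** Recording every operated-knee event under the broad 1.1 definition would take in routine postoperative symptoms for 24 months. The remedy should be narrower than that.

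**Conclusion.** The point holds in limited form. Section 3.1 cannot be reconciled with section 5.3, or with the visit schedule as worded. Followed literally, it leaves a re-rupture judged unrelated, and any other serious event judged unrelated, unrecorded as an event. A reoperation judged not serious may also be missed. Because no other field is specified for these events, knees revised before 24 months may sit unlabelled in the IKDC and KT-1000 comparison.

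No size is claimed, since the documents give no re-rupture or reoperation rate. Counting the classes that 3.1 keeps describes the scope of the rule and says nothing about how many events are missed. Two stronger readings are also unsupported:

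- *That the filter biases the arms.* The documents only leave the PI's masking unstated. They give no direction or mechanism.
- *That these events vanish from the data.* They may still show in KT-1000 or IKDC values or in clinical records, but not as study events.

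The conclusion assumes that the legible answer and checked option in 3.1 are the operative text. It is a cheap improvement and does not challenge the primary design.

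**What to change.** 1. Reconcile 3.1 with the visit schedule and 5.3, so that one recording rule governs and the annual review can be carried out.
2. Record all serious adverse events whatever their judged relatedness. For serious events, the question of how 3.1 treats possible relatedness then no longer affects recording.
3. Add a short field for graft re-rupture and for reoperation of the operated knee (yes/no and date), completed whatever the judged relatedness or seriousness. Collect it at each scheduled follow-up, including home visits, and at both sites, since a table built from UVA alone would omit up to 35 prospective participants.
4. Tabulate these events descriptively by randomized arm.
5. Leave the reporting rules in 3.7 unchanged.

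The cost is one or two extra case-report-form lines per visit and a minor protocol modification. No new visit or test is needed.
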